Official Title: Compensatory Cognitive Training Via Telehealth for Veterans With Alcohol Use Disorders

ClinicalTrials.gov Identifier (NCT Number): NCT06134128

Date of Document: 5/24/2024

Point of Contact: [name]
VA Portland Healthcare System
[contact] [name]
Email:[contact]

Title

Compensatory Cognitive Training Via Telehealth for Veterans with Alcohol Use Disorders

Investigators

[name], M.A. (Co-PI)
[name]. (Co-PI)
[name]. (Co-I)
[name]. (Co-I)

Specific Aims/Purpose

See sponsor/3rd party protocol for information in this section. Indicate what heading/subheading in the 3rd party protocol that the information is located: [REDACTED]

Prior research conducted by our team at the VA Portland Healthcare System (VAPORHCS) has demonstrated that Compensatory Cognitive Training (CCT) reduces cognitive problems and improves compensatory cognitive strategy use among Veterans with a history of mild traumatic brain injury (Pagulayan et al., 2017; Storzbach et al., 2017) and mild cognitive impairment (Huckans et al., 2013; Huckans et al., 2010). Motivationally Enhanced Compensatory Cognitive Training for Addictions (ME-CCT-A) is a promising manualized cognitive rehabilitation therapy for addictions that was developed and piloted by the original developers of CCT (Huckans et al., 2018). This study extends our research by evaluating ME-CCT-A delivered via telehealth in the context of early remission from alcohol use disorder (AUD). The specific aims of the study include:

Aim 1. Evaluate feasibility and acceptability in a pilot trial of ME-CCT-A delivered via telehealth in Veterans in early remission from AUDs.

Hypothesis 1: We hypothesize that ME-CCT-A will be feasible and acceptable in a pilot trial of ME-CCT-A delivered via telehealth.

Aim 2. Assess the preliminary efficacy of ME-CCT-A delivered via telehealth on objective cognitive performance, daily functioning, subjective cognitive complaints, and psychiatric and substance use outcomes.

Hypothesis 2: We hypothesize that ME-CCT-A will improve objective cognitive performance, daily functioning, subjective cognitive complaints, and psychiatric and substance use outcomes in Veterans in early remission from AUDs.

Scientific Rationale and Significance

See sponsor/3rd party protocol for information requested in this section. Indicate what heading/subheading in the 3rd party protocol that the information is located: [REDACTED]

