Alcohol use disorders (AUDs) are highly disabling yet treatable conditions that pose a significant burden to individuals and society due to the high rates of morbidity, mortality, and economic costs associated with the condition. Veterans are at elevated risk for developing AUDs due to high rates of trauma exposure, readjustment stressors, and heavy alcohol consumption normalized within military cultures (Meadows et al., 2022; Straus et al., 2020). AUDs are among the most common psychiatric conditions

nationally; the lifetime prevalence of AUDs is 29.1% with a 12-month prevalence of 13.9% (Grant et al., 2015). Rates of AUDs are even higher among Veterans; the lifetime prevalence of AUDs for Veterans is 35.8% with a 12-month prevalence of 15.1% (Boden & Hoggatt, 2018). According to the Centers for Disease Control, AUDs costs the United States \$249 billion annually (Sacks JJ, 2015). The costs associated with AUDs are numerous, with the largest contributors being healthcare expenses, criminal justice expenses, losses to workplace productivity, and motor vehicle crashes (Rehm & Shield, 2019; Rehm, 2009; Sacks JJ, 2015).

Despite the high prevalence and costs associated with AUDs, treatment rates for the general population remain low with only 17.3% of people with AUDs receiving treatment, indicating a treatment gap of 82.7% (Mekonen et al., 2021). For those who enter treatment, relapse rates for current substance use treatment programs remain very high (~40-60%), often with more than half of individuals relapsing within six months of completing treatment (Moos & Moos, 2006; NIDA, 2020). Treatment rates for AUD within the VA are slightly higher, with approximately 25% of Veterans with an AUD receiving specialty addictions treatment for AUD (Williams et al., 2021).

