Telehealth can play a considerable role in increasing access to evidence-based treatments for Veterans with AUDs. The US Department of Veterans Affairs (VA) has expanded access to virtual visits (i.e., VA Video Connect) throughout the COVID-19 pandemic (Connolly et al., 2021). From February 2020 to November 2020, weekly telehealth visits increased by 1,653% with over 40,000 telehealth visits completed daily (US Department of Veteran Affairs, 2021). Preliminary research indicates that there is little difference between evidenced-based treatments (EBTs) delivered in-person versus via telehealth (Fiacco et al., 2021; Lin et al., 2019; Shigekawa et al., 2018; Young, 2012). A recent rapid review of telehealth for SUDs highlighted strong support for telehealth as an addition to standard care, as it improved abstinence from alcohol and increased treatment retention (Uhl et al., 2022). A systemic review of group-based treatments delivered via telehealth indicated high patient and provider satisfaction and showed similar outcomes to in-person groups (Gentry et al., 2019). Telehealth can eliminate barriers to Veterans accessing EBTs and has many documented advantages, including improved access to EBTs, cost effectiveness, convenience, greater retention of materials, time saving effects, greater privacy, and increased flexibility for both Veterans and providers (Elmitsky CA, 2013; Frost et al., 2022; Kintzle et al., 2022).

Most individuals entering treatment for AUDs present with cognitive deficits across a range of cognitive domains, including attention, memory, and executive functions, and these deficits frequently persist for six months or longer following remission (Bruinen et al., 2019; Glass et al., 2009; Le Berre et al., 2017; Stavro et al., 2013). Cognitive deficits are associated with increased relapse rates, less treatment compliance, and poorer treatment outcomes in individuals seeking substance use treatment (Czapla et al., 2016; Mahoney, 2019; Schmidt et al., 2017). Despite the high rates of cognitive impairments among adults with AUDs and their negative impact on treatment outcomes, current evidence-based pharmacotherapies and behavioral treatments for AUDs do not specifically treat or address cognitive symptoms. Accessible (e.g., brief, manualized, delivered via telehealth) and effective treatments for Veterans with AUDs and cognitive deficits are urgently needed.

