1	Intro and SUD/cognitive functioning psychoeducation	Creating a "home" for important items	Day planner use	Finding a home for the day planner
2	Organization and prospective memory Part I	Time management	Scheduling and concrete goal setting	Practice using the calendar
3	Organization and prospective memory Part II	Daily and weekly planning sessions	Enter lists and activities into the calendar	Follow through with planning sessions
4	Attention and concentration	Paying attention during meetings and conversations	Practicing paying attention during conversations	Active listening once a day
5	Learning and memory	Internal and external memory strategies	Practice memory strategies	Practice using a strategy everyday
6	Problem-solving and cognitive flexibility	Evaluating costs and benefits to identify better choices	6-step problem-solving method	Practice problem-solving with 2 life goals
7	Planning and goal setting	Goal setting	Identify and re-evaluate priorities	Practice planning a goal
8	Skill integration and review	Review, practice, goals, and planning for the future	How to maintain skills and apply them to goals	Provided with additional SUD-related resources

Assessment Protocol: Veterans will complete the virtual assessment battery (see Table 2) at baseline (approximately 0-2 weeks prior to ME-CCT-A) and follow-up (approximately 0-2 weeks following ME-CCT-A completion). The battery consists of performance-based tests of objective cognition functioning and functional capacity and self-report measures of subjective cognitive complaints/functioning, substance use, engagement in targeted lifestyle practices associated with improved cognition, and engagement in protective activities/factors associated with reduced relapse. The Client Satisfaction Questionnaire (CSQ-8) and a series of structured, open-ended questions specific to the study intervention will be included at follow-up to assess Veterans' satisfaction with the virtual CCT intervention. Assessments will take approximately 2 hours.

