Client Satisfaction Questionnaire (CSQ-8)	Satisfaction with the intervention (follow-up only)
Timeline Followback (TLFB)	Alcohol and cannabis consumption over a given time period
Alcohol Use Disorders Identification Test (AUDIT-C)	Alcohol use

ANALYTIC PLAN.

All data analyses will be conducted by study personnel with expertise in statistics, using Excel, SPSS, or other statistical software approved by the VA.

Phase 2, Aim 2 Feasibility and Acceptability: Descriptive statistics will characterize the feasibility of recruiting and retaining Veterans. Recruitment will be deemed feasible if we successfully screen for eligibility 50% of Veterans referred to the study and enroll 75% of screened Veterans who meet all study inclusion criteria. Retention will be deemed successful if we achieve 75% completion for post-treatment assessments. Chi-square tests of association and t-tests will compare demographic and clinical characteristics of successfully versus unsuccessfully recruited and retained Veterans to identify characteristics of Veterans who may require more intensive recruitment or retention efforts in a future trial. Acceptability will be assessed through surveys on treatment satisfaction (i.e., CSQ-8 with additional study-specific items) following group completion. Treatment will be deemed acceptable if $\geq 70\%$ of Veterans score ≥ 24 on the CSQ-8.

Phase 2, Aim 3 Preliminary Efficacy: Descriptive statistics and exploratory analyses will be used to assess the normality of the data and homogeneity of variance. Although our small sample size will limit our power to detect significant differences between pre- and post-treatment measures, we will

conduct preliminary analyses using t-tests to examine whether pre-post changes are in the expected directions. We will examine effect size (Cohen's d) and significance of our measures.

Study Population

See sponsor/3rd party protocol for requested information in this section. Indicate what heading/subheading in the 3rd party protocol that the information is located:

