The proposed study is conducted at a single site. We propose to enroll up to 30 Veterans in this pilot trial. Because our primary purposes are to examine feasibility and acceptability to Veterans with AUD, achieving adequate statistical power is not a primary concern of this pilot clinical trial. Results from this study with a sample size of up to 30, combined with comparisons to similar studies of CCT with other Veteran groups (e.g., those with mild TBI history), will provide adequate information on expected effect size to allow for estimations of statistical power for a future proposal of a larger pilot trial.

Inclusion criteria include: 1) Male and female Veterans (>18 years) who meet criteria for AUD in early remission (>1 month, <12 months remission) based on the DSM-5 (American Psychiatric Association, 2013); 2) Concern about a mild cognitive decline that has been identified by the Veteran or a knowledgeable informant (e.g., SUD treatment providers), and the Veteran wants treatment for their cognitive concerns; and 3) Access to internet and webcam.

Exclusion criteria include: 1) Intoxication or impaired capacity to understand study risks and benefits; 2) Major Neurocognitive Disorder, dementia, or neurodegenerative disorder (e.g., Alzheimer's Disease); and/or 3) Auditory or visual impairments that would prevent ability to participate in the cognitive rehabilitation group or benefit from compensatory strategies.

Eligibility will be established by electronic medical record review and will be confirmed by the Veteran during the initial phone call.

1. VA-SPECIFIC REQUIREMENT (inclusion of non-Veterans):

N/A. The study does not include non-Veterans.

See sponsor/3rd party protocol for requested information in this section. Indicate what heading/subheading in the 3rd party protocol that the information is located:

Subject Identification/Recruitment

See sponsor/3rd party protocol for requested information in this section. Indicate what heading/subheading in the 3rd party protocol that the information is located:

Recruitment, eligibility screening, consenting, study visits, and CCT groups will be conducted by approved clinical research staff. A Waiver of Authorization and Informed Consent Process for Screening/Recruitment Purposes will be obtained to facilitate subject identification and recruitment.

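### All Veterans enter in AUD remission, so a pre-post t-test and Cohen's d on Timeline Followback alcohol use, the only efficacy analysis stated, would not show whether remission held

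*Combined protocol and SAP*

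**What the plan says.** The inclusion criteria (Study Population) require that Veterans "meet criteria for AUD in early remission (>1 month, <12 months remission". Hypothesis 2 (Specific Aims) covers drinking: "We hypothesize that ME-CCT-A will improve objective cognitive performance, daily functioning, subjective cognitive complaints, and psychiatric and substance use outcomes". The Scientific Rationale rests partly on relapse. It describes outcomes after substance use treatment as "often with more than half of individuals relapsing within six months of completing treatment" and adds that "Cognitive deficits are associated with increased relapse rates".

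The measures table describes TLFB as "Alcohol and cannabis consumption over a given time period" and gives no length. AUDIT-C and the Brief Addiction Monitor are also listed. Assessments take place "at baseline (approximately 0-2 weeks prior to ME-CCT-A) and follow-up (approximately 0-2 weeks following ME-CCT-A completion".

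Under Preliminary Efficacy, the Analytic Plan will "conduct preliminary analyses using t-tests to examine whether pre-post changes are in the expected directions", and will look at Cohen's d and significance. Descriptive statistics appear in that paragraph only as checks of normality and variance. No count of Veterans who drink, relapse or stay abstinent is defined. The sample-size text says results, "combined with comparisons to similar studies of CCT with other Veteran groups", will inform expected effect sizes for a later trial.

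**The concern.** In people already in remission, the alcohol question is whether remission holds. A mean change answers it poorly, because the baseline value depends on how far back TLFB reaches.

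- **Window within remission (about 30 days), near-abstinent Veterans.** Baseline is close to zero. The mean can hardly fall, so the hypothesised improvement is almost unobservable. If nobody drinks at either visit, the differences have no variance and t and d are undefined.
- **Window longer than some Veterans' remission.** Pre-remission drinking enters the baseline. The mean is pulled down even if some Veterans relapse, and the amount depends on how many entered early in remission.

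The same number of relapses could therefore read as worsening, no change or improvement. At stake are one component of Hypothesis 2 and the usefulness of an alcohol d if it were carried into planning the next trial.

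**Working it through.** The plan gives no figure to reproduce: the sample of up to 30 has no stated alpha, power, effect or SD.

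**Inputs from the document.** Up to 30 Veterans. The 75% retention target gives 0.75 x 30 = 22.5, taken as 23. Remission at entry is more than 1 and less than 12 months. Visit spacing is 8 weeks plus 0-2 weeks before and 0-2 weeks after, or 56 to 84 days. (Counting first to last session as 49 days would give 49 to 77.)

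**Assumptions not in the document.** Entry uniform over 1-12 months; no drinking in remission; drinking on 50% of days before remission and on one third of days after relapse; relapse time uniform between visits; the same window length at both visits. The relapse rate is set against the Rationale's six-month figure, taken as 50% at a constant rate: 1 - 0.5^(8/26) = 0.192 and 1 - 0.5^(12/26) = 0.274, so 19% to 27% over 8-12 weeks.

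**Step 1: zero baseline, closed form.** If k of n resume at an equal level and the rest stay at zero, with p = k/n, then d = sqrt(p/(1-p)) x sqrt((n-1)/n). For 5 of 23: sqrt(5/18) x sqrt(22/23) = 0.527 x 0.978 = 0.52; t = 0.515 x sqrt(23) = 2.47; p = 0.022. Here d only re-expresses the proportion who resumed.

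**Step 2: simulation (20,000 trials, n = 23).** Mean paired d; positive means more drinking at follow-up.

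| Window | 0% relapse | 10% | 20% | 40% |
|---|---|---|---|---|
| 30 days | undefined | +0.31 | +0.43 | +0.68 |
| 90 days | -0.39 | -0.18 | -0.02 | +0.22 |
| 180 days | -0.76 | -0.66 | -0.58 | -0.42 |

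At 20% relapse the t-test shows significant worsening in about 50% of trials (30 days), significance in either direction in about 4% (90 days), and significant improvement in about 78% (180 days). With 30 days and 10% relapse, d is undefined in about 10% of trials.

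**Step 3: entry mix.** If half enter at 1-3 months, the 90-day d at 20% relapse moves from -0.02 to -0.46. Two 90-day windows would also share 90 - 84 = 6 to 90 - 56 = 34 days.

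**Step 4: sensitivity at 20% relapse.** With 25% or 75% drinking days before remission, the 180-day d is -0.38 or -0.65. With 15% or 60% after relapse, the 30-day d is +0.41 or +0.44. The sign change between short and long windows persists.

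**Step 5: if remission is not abstinence.** With slips on 5% of days throughout, d at 20% relapse is +0.37, -0.03 and -0.57 for 30, 90 and 180 days. If those slips stop after baseline, the 30-day d is -0.40, -0.04 and +0.33 at 10%, 20% and 40% relapse. The 30-day floor therefore depends on near-abstinence.

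**Step 6: would a simple count do better?** Not alone. With continuing 5% slips, the chance of any drinking between visits is 1 - 0.95^56 = 94% to 1 - 0.95^84 = 99%. In simulation the any-drinking count is about 97-98% at 10%, 20% and 40% relapse alike. The count has to be split by baseline drinking.

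**The case against.** The strongest reply has four parts.

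**TLFB is not named in the analysis text.** A reader might infer that the plan commits to a mean TLFB change. It does not: it speaks of its measures generally and defines no TLFB summary variable. Coverage of TLFB is an inference, though no other analysis of substance use is offered.

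**The window may be fixed elsewhere.** A reader might infer that the trial has none. The documents do not support that. Figure 2, which sets out procedures and timeline, and the listed baseline and follow-up interview forms are not visible. A fixed window would reduce the table to one row. It would not in itself supply a drinking-status summary.

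**The mixing is conditional.** A reader might conclude that d always blends window, entry mix and relapse. At about 30 days the window and entry-mix part disappears, because entry requires more than a month of remission. What remains is the floor, which needs near-abstinence, and eligibility does not require abstinence. Nor is d always blind to relapse: with 90 days and uniform entry, the mean falls in 99%, 81%, 55% and 16% of trials at 0%, 10%, 20% and 40% relapse.

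**The stakes are modest.** Feasibility and acceptability are primary, the t-tests are called preliminary, limited power is admitted, and no decision rule uses alcohol. A reader might infer that the next trial will be powered on an alcohol d. The sample-size text does not single out drinking.

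All four points limit the concern. None makes a mean change an answer to whether remission held.

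**Conclusion.** The concern holds in a conditional form. As far as the visible text goes, TLFB alcohol use would be judged by a pre-post t-test and d. Depending on the window, that either sits on a near-zero floor or takes in drinking from before remission. At 20% relapse the illustrative d runs from +0.43 to -0.58. The change of sign is the finding. The exact values rest on assumed drinking levels, uniform entry and a six-month relapse figure that counts from the end of treatment, not from a point 1-12 months into remission.

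The consequence is minor to moderate: one preliminary, secondary outcome, and a poor planning input if its d is reused. TLFB cannabis use and the Brief Addiction Monitor's risk and protective factors are outside this point.

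**What to change.** Do not use the TLFB alcohol t-test or d as the alcohol result. In its place:

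1. Set a baseline TLFB window of about 30 days, which stays within the required remission. Let the follow-up TLFB run from the baseline visit to the follow-up visit.
2. Report the number and percent who drank in that interval with an exact 95% CI, split by whether they drank in the baseline window. Resumed drinking (none at baseline, some afterwards) is then separate from continuing slips.
3. Report drinking days among those who drank.
4. Give bounds over all enrolled Veterans, with missing counted as not drinking and then as drinking. With 5 of 23 drinking and 7 of 30 missing, these are 5/30 = 17% and 12/30 = 40%.
5. Treat AUDIT-C the same way, as descriptive and not as a pre-post d for efficacy.
6. Label the result descriptive, since there is no control group. Carry the percent and its CI, not d, into planning the next trial.

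The cost is about one paragraph and a fixed TLFB interval, with no new instrument, visit or staff. The downsides are recall of up to about 12 weeks, intervals that differ by up to about 4 weeks, and a wide CI (5 of 23: 7% to 44%). The split is also imperfect: with random slips on 5% of days, 0.95^30 = 21% of Veterans would show no drinking in the baseline window by chance, and most would then count as resumed. The drinking days in item 3 help to tell them apart.

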4. The Corporate Data Warehouse (CDW) will be utilized to compile a list of potential participants. IRB-approved study staff will use this list to conduct medical chart reviews (i.e., CPRS) to identify Veterans who meet study criteria, do not meet exclusion criteria, are able to provide informed consent, can attend visits virtually, and may be interested in participating in the research. Veterans who are identified as eligible will be sent a letter from the Mental Health Clinical Director, a letter of introduction from the study team, the study flyer, and a form with the option to opt-in or opt-out to hearing more about the research either by calling study staff or returning the enclosed opt-in/opt-out form. A self-addressed, postage-paid return envelope will be included for the Veteran's convenience. The letter will also state that if study staff does not receive a response within two weeks, the Veteran may be contacted by phone to verify receipt of the letter and be given the option to be mailed a second letter (if not received). Only verification of Veteran's address will be obtained for those who did not receive a letter. Study staff will call all Veterans who indicate interest to provide more information about the study, answer any questions the Veteran may have, and, if applicable, schedule the initial baseline visit.

An appointment confirmation letter will be mailed to a participant after they have scheduled their initial visit. An appointment confirmation letter will also be sent prior to their follow-up visit. If a participant is enrolled in the study and not returning phone calls to schedule additional research visits, a no-show letter will be sent in the mail asking the participant to contact the research coordinator to discuss their interest in their continued involvement in the research study. If the research coordinator does not hear back from the participant within two weeks of sending the letter, the participant will be disenrolled from the research study.

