Inclusion of women and minorities in this pilot study is appropriate and is encouraged. Subject selection is based only on the criteria described in the subject eligibility section. Women and minorities are not excluded from the study solely based on either of those demographic characteristics. Because sex effects may be observed, we will make every effort to enroll equal numbers of men and women. Given that all research participants will be Veterans treated within the VAPORHCS, children will not be included in this study.

Informed Consent & HIPAA Authorization

See sponsor/3rd party protocol for requested information in this section. Indicate what heading/subheading in the 3rd party protocol that the information is located: [REDACTED]

The procedure for collecting informed consent and HIPAA authorization will be conducted via phone, video, mail, or secured/encrypted email as described in these steps:

Preliminary eligibility and screening phone call: For Veterans who are recruited into this study through referrals from clinicians, word of mouth at VAPORHCS, or after seeing a study flier, the research team members will conduct a chart screen and phone call to determine preliminary eligibility. Eligible participants who have given their permission during the screening call with a study staff member will be informed to expect a packet in the mail or electronically via DocuSign. Potential participants will be advised of potential risks when returning signed documents through the mail. A packet containing the Informed Consent Form, HIPAA, subject reimbursement forms, and self-report measures will be sent to their home address (along with a self-addressed, stamped envelope [SASE]) or sent via DocuSign. Informed consent will either be obtained at the end of this call or conducted during a separate pre-arranged phone or video appointment. The packet will contain a reminder for the recipient to not sign the documents prior to their next scheduled contact time with study staff.

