VA REDCap will not be utilized for this study since VA REDCap is an intranet-only application that would require participants to have an active VA network account to be able to complete questionnaires within the application. Instead, OHSU's REDCap server will be utilized to store questionnaire data. Veterans will have the choice of either completing questionnaires online (through OHSU REDCap) or on paper. If the Veteran chooses to complete the questionnaires online, a link to the online questionnaires will be sent in the mail in their appointment confirmation letter. If the Veteran chooses to complete the questionnaires on paper, the paper questionnaires will be sent in the same envelope as their appointment confirmation letter. Only coded data will be stored on OHSU's REDCap application, a highly secure and robust web-based research data collection and management system. The questionnaires will have an alphanumeric code that will be linked to the participants' names in a separate spreadsheet that will remain behind the VA firewall at VAPORHCS. No identifiable information will be entered into REDCap at any time.

Data and Safety Monitoring Plan (DSMP)

See sponsor/3rd party protocol for requested information in this section. Indicate what heading/subheading in the 3rd party protocol that the information is located:

VA-SPECIFIC REQUIREMENTS:

[figure not shown]
Monitoring human participant recruitment, neuropsychiatric data collection, and data entry will be performed by the Co-PIs and study staff. Any adverse events will be reported immediately to the Co-PIs who will evaluate the patient and determine if any additional evaluation or treatment is needed. [name] will ensure that adverse events are properly reported to the IRB. The study staff will examine all cumulative adverse events quarterly to determine if there are any systematic problems. The balance of risk to benefit will be continuously monitored by the Co-PIs, and the study may be modified or terminated if risks begin to outweigh benefit.

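### Do the two descriptions of how the baseline questionnaires reach Veterans put the feasibility or pre-post results at risk?

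*Combined protocol and SAP*

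**What the plan says.** Under Informed Consent & HIPAA Authorization, the paragraph on the screening call says: "A packet containing the Informed Consent Form, HIPAA, subject reimbursement forms, and self-report measures will be sent to their home address" and continues "along with a self-addressed, stamped envelope [SASE]) or sent via DocuSign". It opens by naming some recruitment sources: "For Veterans who are recruited into this study through referrals from clinicians, word of mouth at VAPORHCS, or after seeing a study flier". The packet also carries "a reminder for the recipient to not sign the documents prior to their next scheduled contact time".

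The section on web and mobile applications gives another account: "Veterans will have the choice of either completing questionnaires online (through OHSU REDCap) or on paper". Those who go online find the link in their appointment confirmation letter; for those who prefer paper, "the paper questionnaires will be sent in the same envelope as their appointment confirmation letter". These forms carry a code, and the file linking code to name stays behind the VA firewall.

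The Subject Identification/Recruitment section says when the letter goes out: "An appointment confirmation letter will be mailed to a participant after they have scheduled their initial visit". For the second visit: "An appointment confirmation letter will also be sent prior to their follow-up visit".

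The measures table under Research Design and Methods uses self-report measures and questionnaire battery as names for the same group of instruments. The Assessment Protocol there has the battery completed within about two weeks before treatment starts and again within about two weeks after it ends.

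**The concern.** Both descriptions reach the baseline visit. The packet goes out around screening and consent, so it can serve only baseline. The confirmation letter goes out for both visits, so the application section covers baseline as well as follow-up. Neither section refers to the other.

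Read literally, a Veteran could receive two baseline sets, at different times and by different electronic routes, with no statement of which set is scored. Three things would then be at stake:

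- **Feasibility.** The Overview lists the workability of testing and data collection among the things to be assessed. Two procedures would blur what was tested.
- **Pre-post change.** Packet delivery at baseline and letter delivery at follow-up would change route and lead time within a Veteran. A single-arm design cannot separate that from change over treatment.
- **Confidentiality.** A DocuSign packet would put alcohol and drug questionnaires next to signed, named forms, whereas the REDCap route holds coded data only.

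**Working it through.** The plan states no figure on this point, so the check is a comparison of sections plus simple counts.

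**Instruments affected.** The measures table lists 8 self-report measures. The CSQ-8 is for follow-up only, so 8 − 1 = 7 are due at baseline and at both visits. It lists 10 neuropsychological tests. The WRAT5 is for baseline only, so 10 − 1 = 9 are given twice. The share is 7 / (7 + 9) = 7/16 = 43.75%. This measures how much of the battery the wording covers, not the size of any error.

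**Routes.** The consent section allows paper by mail or DocuSign. The application section allows paper by mail or REDCap. Three routes are named in all and one, paper, is common to both. The direct contradiction is therefore the electronic route.

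**Timing.** Sending a form is not completing it. The Assessment Protocol window applies to the whole battery, questionnaires included. If the visit takes place v days before session 1, the room left before the visit is 14 − v days: 14, 7 and 0 days for v = 0, 7 and 14. A form filled in earlier than that would be outside the approximate window whichever envelope it came in. The window rules this out; the choice of envelope does not.

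**One mailing or two.** The packet's reminder about signing presupposes that a next contact is already booked. Consent may be taken at the end of the screening call or at a separate appointment. If the baseline visit is booked on that call, packet and letter can share an envelope. If both sections were followed separately, 2 × 7 = 14 forms would go out instead of 7, but no section asks for two sets to be completed or scored.

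**Effect on the stated criteria.** The Analytic Plan has four numeric criteria:

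| Criterion | Uses a baseline questionnaire score? |
|---|---|
| 50% of referred Veterans screened | No |
| 75% of eligible screened Veterans enrolled | No |
| 75% completing post-treatment assessments | No |
| At least 70% scoring 24 or more on the CSQ-8 | No; this form is given at follow-up only |

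**Effect on the pre-post analysis.** The application section on its own lets a Veteran use paper at one visit and REDCap at the other. Within-person change of mode is therefore possible whether or not the measures are in the consent packet, and removing them would leave it in place.

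**The case for a change.** The strongest case for a change is that the application section offers a closed choice of two modes and DocuSign is not one of them. A single envelope would not cure that, and no visible text says which section governs. The packet's reminder concerns signing, not filling in questionnaires. Completion date also matters for an instrument such as the Timeline Followback, which asks about a set period. The edit would be cheap.

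The mismatch over DocuSign stands. The consequences drawn from it do not:

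- **Feasibility.** The plan never intended one collection method, since the choice between paper and online is deliberate, and no criterion is set for questionnaire delivery.
- **Timing.** The battery window already governs completion dates, for the Timeline Followback as for the rest.
- **Confidentiality.** The consent section describes return by DocuSign or envelope for signed documents; nothing says completed questionnaires come back that way. The sections on privacy and on information management add locked storage for paper and keep consents and the linking key apart from the de-identified data.
- **Recruitment source.** The consent section gives the only visible consent procedure. If it excluded Veterans found through the data warehouse, they would have no described route to consent. The sensible reading is that it applies to everyone.

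Taking the measures out of the packet also has a cost. The packet is the only mailing of these forms with a stated return envelope.

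**Conclusion.** This is a clerical slip about how forms are sent. Study staff can resolve it by following the Assessment Protocol window and the application section, which already cover both visits. It concerns 7 of 16 repeated instruments but alters none of the four numeric criteria, no test and no effect size calculation. Dating each form and recording its route would be harmless, but no gain in any planned result has been shown.

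The conclusion assumes that questionnaires are completed within the stated window and that one set per visit is scored; nothing in the text points the other way. No completion dates or accrual rates are given, so neither a share of out-of-window forms nor a shift in Cohen's d can be estimated. The procedures figure and the confirmation letters, which are not visible here, may already settle the sequence of mailings. The pre-post analyses are described as preliminary and look mainly at the direction of change, which further limits what a difference in delivery route could do to the conclusions.
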